2. OBJECTIVES

Primary Objective: To describe the patient and tumor characteristics, first course treatments, survival and subsequent primary malignancies of children and adolescents diagnosed with primary gastrointestinal malignancies.

Secondary Objective(s): 1) To investigate time trends in incidence, stage at diagnosis, first course treatments, mortality, and overall survival. 2) To explore independent prognostic factors for overall survival. 3) To calculate the standardized incidence of second primary malignancies in childhood and adolescent gastrointestinal cancer survivors, relative to the general population.

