CRC	ICD-O-3 C018.0-C018.9, C019.9, C020.9	AJCC stage I-IV	ICD-O-3 Grade I-IV	ICD-O-3 Cat. 1: 8140 (AC, NOS), Cat. 2: 8210 + 8220 + 8221 + 8261 + 8263 (AC in polyp/adenoma), Cat. 3: 8480-8482 (MAC), Cat. 4: 8490 (SRCC), Cat. 5: remaining cases (others/unknown) ¹⁶	Yes (values 10-90); No or unknown (values 0 and 99)	NR	Yes (all subtypes); No or unknown (incl. "refused" and "recommended, unknown if administered")	Yes; No or unknown

New abbreviations: NR, not relevant; N/A, not available; Cat, category; AC, adenocarcinoma; MAC, mucinous adenocarcinoma; SRCC, signet ring cell carcinoma.

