8.1.2 Secondary study parameters/endpoints

1. Time trends in incidence, stage at diagnosis, first course treatments, mortality, and overall survival.
2. Associations between the variables age at diagnosis, sex, race and origin, year of diagnosis, stage at diagnosis, and histologic category (when relevant) with overall survival in multivariable analysis.
3. Standardized incidence of second primary malignancies in patients who survived (i) two or more months, or (ii) five or more years after gastrointestinal cancer diagnosis, relative to the general U.S. population.

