10.1 Primary study parameter(s)

Data is presented quantitatively (numerically). Continuous variables are summarized with medians and ranges, and categorical variables are summarized with frequencies and proportions. Age at diagnosis can also be summarized with frequencies and proportions, using 1-year age categories. Overall survival (OS) is estimated by the Kaplan-Meier method. OS is defined as the time from the date of

diagnosis until the date of death from any cause (event) or until the date of last follow-up. Survival curves may be compared with the log-rank test. Median follow-up is estimated using the reverse Kaplan-Meier method³².

The following descriptive statistics are minimally obtained:

Frequencies and proportions of the different gastrointestinal malignancies – specified in Table 2 – by age group (<18; 18-24 years at diagnosis) and by 1-year age categories (0-24 years). Age distributions of patients diagnosed with common gastrointestinal malignancies (BL, UESL, NEN, HCC, HB, GC, and CRC).

Stratified by age group (<18; 18-24 years at diagnosis):

Frequencies and proportions of the different gastrointestinal malignancies by primary anatomic site (ICD-O-3 topography codes C015-C026). Summarized sex and race and origin data of patients diagnosed with common gastrointestinal malignancies. Frequencies and proportions of surgery, radiation, and chemotherapy as part of the first course of treatment of patients with common gastrointestinal malignancies. Frequencies and proportions of different stages at diagnosis, different grades, and different histologic subtypes of patients diagnosed with CRC. Frequencies and proportions of CRC cases by primary anatomic site (ICD-O-3 topography codes C018.0-C018.9, C019.9, and C020.9). Kaplan-Meier curves depicting OS of patients diagnosed with common gastrointestinal malignancies. Estimated 1- and 5-year OS (with 95% confidence intervals) of patients diagnosed with common gastrointestinal malignancies. Kaplan-Meier curves depicting OS of CRC patients by i) stage at diagnosis, ii) by grade, and iii) by histologic subtype. Frequencies and proportions of patients with multiple primary cancers registered in 2000-2019 by common cancer subgroup (Table 3). Median total number of in situ/malignant tumors of patients diagnosed with common gastrointestinal malignancies.

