Trends over time in OS of patients with common GI malignancies are evaluated by Cox regression analysis, with year of diagnosis as a continuous variable. The estimated 1- and 5-year OS of patients with common GI malignancies are plotted as percentages by diagnostic time period. For the diagnostic period 2015-2019, 5-year OS is not available due to insufficient follow-up. In addition, changes over

time in OS of patients diagnosed with common GI malignancies may be visualized by plotting separate Kaplan-Meier curves for each diagnostic time period¹⁶.

To explore independent prognostic factors for overall survival of patients with common GI malignancies, multivariable Cox regression analysis is performed with age at diagnosis, sex, race and origin, year of diagnosis, stage at diagnosis, and histologic category (when relevant; see Table 3) as included variables.

Table 4. Multivariable Cox regression analysis

	BL			UESL			NEN			HB			HCC			GC			CRC		
	No. at risk	HR (95% CI)	P	No. at risk	HR (95% CI)	P	No. at risk	HR (95% CI)	P	No. at risk	HR (95% CI)	P	No. at risk	HR (95% CI)	P	No. at risk	HR (95% CI)	P	No. at risk	HR (95% CI)	P
Age at diagnosis																					
Sex																					
Male		Reference			Reference			Reference			Reference			Reference			Reference			Reference	
Female																					
Race & origin																					
NH-White		Reference			Reference			Reference			Reference			Reference			Reference			Reference	
NH-Black																					
NH-Other/Unknown																					
Hispanic																					
Year of diagnosis																					
Stage																					
Localized																					
Regional		Reference			Reference			Reference			Reference			Reference			Reference			Reference	
Distant																					
Unknown/unstaged																					
Histology																					
Category 1		NR			NR						NR										
Category 2								Reference						Reference						Reference	
Category 3																					
Category 4																					
Category 5																					

NH, non-Hispanic; NR, not relevant

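### For colorectal carcinoma, survival is plotted by grade but grade is not in the multivariable Cox model, so its independent association with survival is not estimated and the histology hazard ratios are not adjusted for it

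*Combined protocol and SAP*

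**What the plan says.** Section 10.1 lists, as part of the descriptive primary objective, "Kaplan-Meier curves depicting OS of CRC patients by i) stage at diagnosis, ii) by grade, and iii) by histologic subtype". The only comparison attached to these curves is optional: "Survival curves may be compared with the log-rank test". CRC is the only cancer for which curves by grade are planned.

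Section 2 gives as a secondary objective "To explore independent prognostic factors for overall survival". Section 10.2 carries this out: "multivariable Cox regression analysis is performed with age at diagnosis, sex, race and origin, year of diagnosis, stage at diagnosis, and histologic category". Section 8.1.2 gives the same list, ending with "year of diagnosis, stage at diagnosis, and histologic category (when relevant) with overall survival in multivariable analysis", and the Summary repeats it. Table 4, the shell for the results, has no grade row for any tumour.

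Table 3 (section 8) defines grade for CRC as "ICD-O-3 Grade I-IV", in a column separate from histology. Table 1 shows that grade is retrieved: one item through 2017, then separate clinical and pathological items from 2018. Section 10 limits analyses using either histologic subgroups or grade to microscopically confirmed cases.

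**The concern.** The plan picks out three tumour factors for CRC survival. Two of them, stage and histology, go on to the adjusted model; grade stops at unadjusted curves. A difference between curves by grade could be due to stage, histology or age, so the curves cannot show whether grade is an independent prognostic factor, which is what the secondary objective asks.

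The second consequence concerns histology. A hazard ratio between two histologic categories from the planned model compares patients alike in age, sex, race and origin, year and stage, but not in grade. If one category contains more high-grade tumours, and grade is related to survival given stage, part of that hazard ratio reflects grade. A reader of Table 4 could not tell how much.

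At stake is whether the paper can say that grade matters beyond stage and histology, or that histology matters beyond grade.

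**Working it through.** The documents state no sample size, death count or hazard ratio, so there is no figure of the plan to reproduce.

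**1. Where each factor appears for CRC**

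| Factor | Survival curves (10.1) | Cox covariate (Summary, 8.1.2, 10.2) | Row in Table 4 |
|---|---|---|---|
| Stage | yes | yes | yes |
| Histologic category | yes | yes | yes |
| Grade | yes | no | no |

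Differentiation does not enter the CRC model by another route: the CRC histology categories in Table 3 are built from morphology codes. For neuroendocrine neoplasms, by contrast, the histology categories are themselves defined by differentiation.

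**2. How far a histology hazard ratio could shift**

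All inputs here are assumptions. Let p1 and p0 be the proportions of high-grade tumours in two histologic groups among patients alike on the other covariates, including stage. Let H be the hazard ratio for high versus low grade. At the start of follow-up, leaving grade out multiplies the histology hazard ratio by

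(p1 × H + 1 − p1) / (p0 × H + 1 − p0).

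| p1 vs p0 | H = 1.4 | H = 1.8 | H = 2.2 |
|---|---|---|---|
| 20% vs 20% | 1.00 | 1.00 | 1.00 |
| 40% vs 20% | 1.16/1.08 = 1.07 | 1.32/1.16 = 1.14 | 1.48/1.24 = 1.19 |
| 70% vs 20% | 1.28/1.08 = 1.19 | 1.56/1.16 = 1.34 | 1.84/1.24 = 1.48 |

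**3. Check by simulated Cox fits**

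Assumed: 6,000 patients and one run per scenario, a binary histology with 15% prevalence and true hazard ratio 1.5, and binary grade.

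- If grade has no effect, the histology hazard ratio changes by at most 0.01 when grade is left out.
- If high grade is equally common (30% vs 30%), the change is at most 0.08, even at H = 3 (1.40 without grade, 1.48 with).
- At 80% vs 30%, the hazard ratio without versus with grade is 1.82 vs 1.46 (H = 1.5), 1.97 vs 1.43 (H = 2) and 2.39 vs 1.49 (H = 3). The ratios are 1.25, 1.38 and 1.60; the formula gives 1.4/1.15 = 1.22, 1.8/1.3 = 1.38 and 2.6/1.6 = 1.63.
- At 50% vs 30% and H = 3, it is 1.74 vs 1.53, a ratio of 1.14, against 2.0/1.6 = 1.25 from the formula. The formula can therefore overstate the shift over a full follow-up.

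**4. Size of the model**

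Parameters in the planned CRC model, from Tables 3 and 4: age 1, sex 1, race and origin 3, year 1, stage 3, histology 4; total 13. Grade as I-II, III-IV or unknown adds 2, giving 15. At an assumed 10 deaths per parameter, the deaths wanted rise from 130 to 150; at 5 per parameter, from 65 to 75. These apply to each age stratum if the model is fitted by stratum.

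**The case against.** The covariate list is the same in the Summary, 8.1.2, 10.2 and Table 4, and is one template for seven cancers, for two of which Table 3 marks grade as not relevant. The curves serve a descriptive objective and the model an exploratory one. Nothing promises that every plotted factor will be modelled, and first-course treatment and CRC primary site are also left out. This stands: the omission is an unexplained modelling choice. A reader might infer that the plan contradicts itself, but the documents do not support that.

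A reader might also infer that the CRC histology hazard ratios do carry the effect of grade and are inflated. The documents do not support that either. It needs grade to be linked to histology and, given stage, to survival, and they give neither link. If poor differentiation is partly a feature of a histologic type, the hazard ratio without grade is a legitimate overall difference between types. That is a reason to report both versions. It does not supply the missing estimate for grade.

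The size of the shift also depends on the contrast. As its text reads here, Table 4 seems to place the CRC histology reference at category 2, though its layout is uncertain. The factors above are for a generic pair of categories and cannot be carried over to a particular row.

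Finally, sparse data could justify a short covariate list. Section 10.2 presents results separately for patients under 18 and aged 18-24, and deaths in the younger stratum may be few. No counts are given, so this can be neither confirmed nor dismissed. It bears on how the extra model is fitted.

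**Conclusion.** The concern holds in a limited form. Under the plan, grade in CRC receives only an unadjusted survival comparison, so its independent association with survival is not estimated although the objective is "To explore independent prognostic factors for overall survival of patients with common GI malignancies". The histology hazard ratios are not adjusted for grade and may partly reflect it.

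How far they do is unknown. With assumed grade hazard ratios of 1.4 to 2.2, the factor runs from 1.00 (no imbalance in grade) through 1.07 to 1.19 (40% vs 20%) to 1.19 to 1.48 (70% vs 20%), with both inputs understood as conditional on stage and the other covariates. The planned model is not thereby wrong. The gap is worth closing because the data are already retrieved and the cost is small.

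**What to change.** Keep the planned model, and add to section 10.2 and Table 4:

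- A pre-specified CRC sensitivity model with the same covariates plus grade as I-II, III-IV or unknown. Report the histology hazard ratios from both models side by side, with the adjusted hazard ratio for grade.
- A rule for combining the grade item that runs through 2017 with the separate clinical and pathological items from 2018. The planned curves by grade need this rule as well.
- A rule that, where the age strata have too few deaths, this model is fitted in the combined 0-24 group and the report says so. Section 8 already allows combined analyses if clearly stated.

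Because histology and grade analyses share the microscopic-confirmation restriction, keeping an unknown-grade level loses no further cases.

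The cost is one more Cox fit, or two if done by age stratum, and two more coefficients in each. Some correlation between grade and histology will widen intervals, and the unknown-grade level may be related to year of diagnosis through the 2018 change of items. If the model is not added, the least that is needed is a sentence saying why grade is left out and that the histology hazard ratios are not adjusted for it.

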10.2 Secondary study parameter(s)

Data will be presented quantitatively (numerically); stratified by age group (<18; 18-24 years at diagnosis).

Age-adjusted incidence and mortality rates are calculated as the average annual number of cases or deaths per million person-years at risk, respectively. For mortality rates, calendar year and age (<18; 18-24 years) represent year and age at death, respectively. Incidence rates of the common gastrointestinal malignancies are based on SEER 17 incidence data (2000-2019); mortality rates of malignant neoplasms of the digestive organs (ICD-O-3 topography codes C015-C026) are based on mortality data of the total U.S. population (1969-2019). In addition, incidence-based mortality (IBM) rates – for cases registered in SEER 17 – may be calculated to partition mortality by digestive cancer subtype (BL, UESL, NEN, HCC, HB, GC, and CRC)³³. The annual population size is obtained from the Census Bureau. Rates are age-standardized using the age structure of the 2000 U.S. standard population. Rates are calculated using SEER*Stat software and plotted using 3-year moving averages³⁴. When 3-year moving averages vary greatly, rates may be plotted using 5- or 7-year moving averages. Trends over time in incidence and mortality are analyzed by Poisson regression, with the calendar year as a continuous regressor variable. In addition, trends over time may be evaluated by linear regression modelling – a method frequently used in prior studies^{34,35} – to allow easier comparisons between studies, as well as with Jointpoint regression modelling to identify change points in the trends. Results are reported as average annual percent changes (AAPC) along with 95% confidence intervals and *P* values.

Trends over time in stage at diagnosis or first course treatments of patients with common GI malignancies are tested with logistic regression, with year of diagnosis as a continuous variable³⁴. The proportions of each stage at diagnosis or treatment category are plotted as weighted 3-year moving averages in percentages. When weighted 3-year moving averages vary greatly, results may be plotted using weighted 5- or 7-year moving averages.

Trends over time in OS of patients with common GI malignancies are evaluated by Cox regression analysis, with year of diagnosis as a continuous variable. The estimated 1- and 5-year OS of patients with common GI malignancies are plotted as percentages by diagnostic time period. For the diagnostic period 2015-2019, 5-year OS is not available due to insufficient follow-up. In addition, changes over

time in OS of patients diagnosed with common GI malignancies may be visualized by plotting separate Kaplan-Meier curves for each diagnostic time period¹⁶.

To explore independent prognostic factors for overall survival of patients with common GI malignancies, multivariable Cox regression analysis is performed with age at diagnosis, sex, race and origin, year of diagnosis, stage at diagnosis, and histologic category (when relevant; see Table 3) as included variables.

Table 4. Multivariable Cox regression analysis

	BL			UESL			NEN			HB			HCC			GC			CRC		
	No. at risk	HR (95% CI)	P	No. at risk	HR (95% CI)	P	No. at risk	HR (95% CI)	P	No. at risk	HR (95% CI)	P	No. at risk	HR (95% CI)	P	No. at risk	HR (95% CI)	P	No. at risk	HR (95% CI)	P
Age at diagnosis																					
Sex																					
Male		Reference			Reference			Reference			Reference			Reference			Reference			Reference	
Female																					
Race & origin																					
NH-White		Reference			Reference			Reference			Reference			Reference			Reference			Reference	
NH-Black																					
NH-Other/Unknown																					
Hispanic																					
Year of diagnosis																					
Stage																					
Localized																					
Regional		Reference			Reference			Reference			Reference			Reference			Reference			Reference	
Distant																					
Unknown/unstaged																					
Histology																					
Category 1		NR			NR						NR										
Category 2								Reference						Reference						Reference	
Category 3																					
Category 4																					
Category 5																					

NH, non-Hispanic; NR, not relevant

Standardized incidence ratios (SIR) and 95% confidence intervals of second primary malignancies (SPM) in patients that survived i) two or more months, or ii) five or more years after initial gastrointestinal cancer diagnosis are estimated using the multiple primary (MP-SIR) session of SEER*Stat software. Analyses are performed by common gastrointestinal cancer subgroup (BL, UESL, NEN, HCC, HB, GC, and CRC). SIR calculations compare the observed second cancer incidence with the expected first primary cancer incidence in the age-, sex-, race- and calendar year-matched general population²⁹. The general population rates are available by cancer site, 5-year age categories, sex, race and 5-year diagnostic time periods.

A *P* value < 0.05 is considered statistically significant.

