3. STUDY DESIGN

This is an observational population-based cohort study based on publicly available data of the Surveillance, Epidemiology, and End Results (SEER) database. The SEER Program collects cancer incidence and survival data from multiple population-based cancer registries in the United States of America (U.S.). SEER began collecting data in 1973 with a limited number of registries. Since 1973, the SEER Program has been expanded to cover numerous additional areas. SEER 17 is the largest registry grouping with complete data, and includes cancer cases registered from 2000 onwards in 17 cancer registries covering approximately 26.5% of the U.S. population (<https://seer.cancer.gov/registries/data.html>). Importantly, SEER recommends that when performing an analysis, researchers subset based on year or registry so that they have consistent geographic coverage for the period of the analysis. Accordingly, SEER does not provide datasets with varying registries and years of data (e.g. 1975-2000 data from SEER 8 registries and 2000-2019 data from SEER 17 registries). SEER 17 incidence data is used for this study, because the SEER 17 database contains the most cancer cases to investigate, when compared to SEER 12 (1992-2019) or SEER 8 (1975-2019) (<https://seer.cancer.gov/data-software/documentation/seerstat/nov2021/>).

The SEER Program registries routinely collect data on patient demographics, primary tumor site, tumor morphology, stage at diagnosis, first course of treatment, and follow-up for vital status. The mortality data reported by SEER are provided by the National Center for Health Statistics (NCHS). Notably, NCHS granted SEER permission to make available mortality data of the total U.S. population – based on death certificates – for the period 1969-2019. The population data used in calculating cancer rates is obtained from the Census Bureau.

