4. STUDY POPULATION

4.1 Population (base)

All cases registered in the SEER 17 database between (and including) 2000 and 2019 (last data year in the April 2022 SEER data release).

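### If subtype incidence-based mortality is calculated from SEER 17, deaths in the first calendar years are under-counted and the mortality trend is biased upward

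*Combined protocol and SAP*

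**What the plan says.** Section 10.2 sets up two kinds of mortality rate. The main one covers all malignant neoplasms of the digestive organs together and uses national death data for 1969-2019. The second is optional: "incidence-based mortality (IBM) rates – for cases registered in SEER 17 – may be calculated to partition mortality by digestive cancer subtype", with seven subtypes listed.

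Three other statements decide how the second rate behaves:

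- Source of cases. Section 3 says that SEER 17 "includes cancer cases registered from 2000 onwards in 17 cancer registries", and section 4.1 defines the study base as "All cases registered in the SEER 17 database between (and including) 2000 and 2019".
- Time axis. Section 10.2: "For mortality rates, calendar year and age (<18; 18-24 years) represent year and age at death, respectively".
- Trend model. Section 10.2: "Trends over time in incidence and mortality are analyzed by Poisson regression, with the calendar year as a continuous regressor variable". Results are given as average annual percent changes (AAPC) with confidence intervals and P values. Moving-average plots are planned, and linear and joinpoint models are optional additions.

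Neither section 10.2 nor any other part of the document gives incidence-based mortality (IBM) a first year of death, a run-in, a fixed interval from diagnosis to death, or a stated limitation.

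**The concern.** IBM counts a death only if the patient's diagnosis is in the registry file. With diagnoses starting in 2000 and deaths indexed by calendar year, the first years contain only deaths that followed diagnosis very quickly. Deaths in those years among patients diagnosed before 2000 are missing, while the population denominator is complete. The shortfall shrinks each year, so a constant true rate looks like a rising one. The deaths lost are those in early calendar years; deaths soon after diagnosis are captured.

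IBM is the only subtype-specific mortality rate in the plan. A registry start-up effect could be reported as rising mortality from, say, colorectal carcinoma in young people, or could hide a real fall. Joinpoint modelling is exposed too: capture climbs steeply and then levels off, which invites a false change point in the early 2000s.

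**Working it through.** The plan gives no IBM figure to reproduce, so the check is a model of the planned analysis.

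**From the documents:** diagnoses 2000-2019 (sections 3 and 4.1); deaths indexed by year of death, with a log-linear Poisson trend on calendar year (section 10.2); significance at P < 0.05 (end of section 10.2).

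**Assumed, because the documents give no times to death and no counts:** constant incidence and survival (true trend zero); exponential time from diagnosis to death among fatal cases, with median m; series starting in 2000.

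**Captured share.** Let λ = ln 2 / m, and let k = 0 for 2000, 1 for 2001, and so on. The share of that year's deaths whose diagnosis falls in 2000 or later is

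c(k) = G(k+1) − G(k), with G(t) = t − (1 − exp(−λt))/λ.

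Example with m = 1 year, λ = 0.6931:

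- G(1) = 1 − 0.5/0.6931 = 0.279
- G(2) = 2 − 0.75/0.6931 = 0.918
- G(3) = 3 − 0.875/0.6931 = 1.738
- Shares for 2000, 2001 and 2002: 0.279, 0.639 and 0.820. Their mean is 0.579.
- 20-year mean share: G(20)/20 = (20 − 1.443)/20 = 0.928, a 7% understatement.

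**Trend.** The planned Poisson model was fitted to c(0), ..., c(19). For the true-decline row, the rate of fatal diagnoses falls 2% per year.

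| Median time to death | 0.5 y | 1 y | 2 y |
|---|---|---|---|
| Captured share 2000 / 2001 / 2002 | 0.46 / 0.86 / 0.97 | 0.28 / 0.64 / 0.82 | 0.15 / 0.40 / 0.58 |
| First 3-year average, % of true rate | 76 | 58 | 38 |
| Understatement of 20-year mean | 4% | 7% | 14% |
| Apparent AAPC, true value 0 | +1.0% | +2.0% | +3.7% |
| Apparent AAPC, true value −2% | −0.8% | +0.3% | +2.1% |

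**Sensitivity.**

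- A wider range of medians, 0.25 to 5 years, gives +0.5% to +6.7% per year. A Weibull time to death with shape 0.7 gives +0.75% to +5.5% over the same medians.
- Strata defined by age at death, as section 10.2 requires, with incidence flat or rising with age (exponential slope 0 to 0.3 per year), give +1.4% to +3.7% for medians of 1 to 2 years.
- The sign is positive in every scenario.

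**Chance of P < 0.05 when the true trend is zero.** With z = slope/SE from the Poisson fit, the chance is P(|Z + z| > 1.96), where Z is standard normal.

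| True deaths per year in the series | 0.5 y | 1 y | 2 y |
|---|---|---|---|
| 2 | 7% | 11% | 23% |
| 5 | 9% | 20% | 48% |
| 10 | 13% | 34% | 77% |

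**Remedies in the same model.**

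- Deaths from 2005 onward, within 60 months of diagnosis: every death year has the same captured share, 1 − exp(−5λ), so the artefact is 0.0% per year. The share of deaths excluded is exp(−5λ): 3% at m = 1, 10% at m = 1.5 and 18% at m = 2.
- A 2005 start without the 60-month limit: the residual is +0.1% per year at m = 1 and +0.9% at m = 2.

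**The case against.** The strongest reply is that the problem is twice conditional. IBM is optional, and its stated purpose is to split mortality by subtype; the plan never says outright that IBM trends will be tested or that the series starts in 2000. If IBM gives only whole-period subtype shares, there is no trend bias, merely some under-representation of subtypes that kill more slowly. The declared mortality-trend endpoint rests on the national series. Subtype survival over time is "evaluated by Cox regression analysis, with year of diagnosis as a continuous variable". Neither is touched.

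That limits the reach of the point but does not remove it. The general sentence on mortality trends covers IBM as written, and the planned moving-average plots would show the artefact even without a test.

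A second reply is that the sizes rest on assumptions. This stands. For a rapidly fatal subtype the effect is small: at a median of 0.25 years the false slope is +0.5% per year and the chance of a false positive stays at 5-7%. The documents do not show that any of the up to 14 series (7 subtypes × 2 age groups) reaches 10 deaths per year. Sparse data limit how often the artefact becomes significant; they do not reduce the bias.

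A third reply is that the source cited for the IBM method may specify a look-back. It could not be consulted, and the plan itself does not adopt one.

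**Conclusion.** The concern holds. If IBM trends are run as section 10.2 is written, with a series from 2000, the slope is biased upward and the mean level downward. The direction follows from the design and needs only that some deaths occur after an interval from diagnosis. The size is illustrative and varies by subtype: about +1% to +4% per year for median times to death of 0.5 to 2 years under constant incidence and survival. That is enough to turn a true 2% annual fall into an apparent rise once the median reaches about a year. A steep enough true decline would still show as a decline.

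This should be corrected before any IBM analysis. It affects an optional secondary analysis and leaves the primary objective, the 1969-2019 national mortality trend and the survival trends by year of diagnosis unchanged.

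**What to change.** Add one sentence to section 10.2:

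> If IBM is calculated, rates, plots and trend tests are restricted to deaths in 2005-2019 occurring within 60 months of a diagnosis made in 2000 or later, and are labelled 5-year IBM.

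Survival months and year of diagnosis are already among the data items in Table 1.

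The cost is five of the 20 calendar years, the loss of deaths beyond 60 months, and a changed estimand, which is why the label matters. For rare subtypes the lost years also reduce precision.

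A simpler alternative is a 2005 start without the 60-month limit. It keeps the later deaths but leaves a small upward residual, which should be reported as a limitation. A shorter run-in suits only rapidly fatal subtypes: a 2002 start leaves about +0.1% per year at a median of 0.5 years, +0.6% at 1 year and +2.0% at 2 years. Whichever rule is chosen should be fixed before the IBM rates are examined.

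### The committed trend model for the 1969-2019 U.S. mortality series allows no extra-Poisson variation and fits one slope to 51 years, so its AAPC intervals may be too narrow and its summary poor

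*Combined protocol and SAP*

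**What the plan says.** Section 10.2 (Secondary study parameter(s)) gives one committed trend model: "Trends over time in incidence and mortality are analyzed by Poisson regression, with the calendar year as a continuous regressor variable". It serves two very different series. "Incidence rates of the common gastrointestinal malignancies are based on SEER 17 incidence data (2000-2019"), which is 20 annual points split by cancer subtype. Mortality rates for all digestive organs "are based on mortality data of the total U.S. population (1969-2019"), which is 51 annual points nationally.

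The secondary results are "stratified by age group (<18; 18-24 years at diagnosis"), with age at death replacing age at diagnosis for mortality. On the rates themselves: "Rates are age-standardized using the age structure of the 2000 U.S. standard population" and "The annual population size is obtained from the Census Bureau".

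Two further models are offered as optional additions. One is linear regression, included for comparability with other studies. The other is described "as well as with Jointpoint regression modelling to identify change points in the trends". On output: "Results are reported as average annual percent changes (AAPC) along with 95% confidence intervals", together with P values. The section's significance threshold is 0.05.

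The section does not state whether the response is counts, crude rates or standardised rates. It also names no population offset, age term, dispersion check, scaled or robust variance, or negative binomial alternative.

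**The concern.** Ordinary Poisson regression fixes the variance at the mean. With a handful of cases a year this hardly matters, because Poisson noise swamps everything else. With large annual counts, modest real variation between years is no longer negligible. The model-based standard error is then too small, the AAPC interval too short, and the 5% error rate is not held. The national mortality series is the one where this can happen.

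Two other weaknesses are separate from interval width. A single log-linear slope over 51 years is a strong assumption, and the only tool in the plan that would detect a change of direction is optional. And because the response and age handling are not stated, two analysts could both follow Section 10.2 and report different AAPCs, one of which might not correspond to the age-standardised rates being plotted.

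Time trends in incidence and mortality belong to the first secondary objective, and the AAPC with its interval and P value is the reported result.

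**Working it through.** The plan states no annual counts, dispersion, AAPC or interval width, so there is no figure of its own to reproduce. Only the series lengths come from the documents: 2019 − 1969 + 1 = 51 years for mortality and 2019 − 2000 + 1 = 20 for incidence. Everything else below is an assumption, shown as a range.

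**1. Extra-Poisson variation.** Let μ be the mean annual count in a stratum and c the extra year-to-year coefficient of variation. The dispersion is φ = 1 + μc². With a flat trend, the nominal two-sided 5% test rejects with probability 2[1 − Φ(1.96/√φ)].

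| μ | φ, c = 5% | rejects | φ, c = 10% | rejects |
|---|---|---|---|---|
| 2 | 1.005 | 5.1% | 1.02 | 5.2% |
| 10 | 1.025 | 5.3% | 1.10 | 6.2% |
| 50 | 1.125 | 6.5% | 1.50 | 11% |
| 100 | 1.25 | 8.0% | 2.00 | 16.6% |
| 200 | 1.50 | 11% | 3.00 | 25.8% |

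Simulated 51-year gamma-Poisson series with c = 10% agree: about 10-13% at 50 deaths, 16-17% at 100 and 25-26% at 200. Multiplying the standard error by the square root of (Pearson χ²/residual df) gives about 4-7%.

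**2. One slope through two.** Assume a decline of 2% or 3% per year (log scale) from 1969 to 1994, then a flat trend or a rise of 1% to 2019. Each segment spans 25 years, so the true average annual change is exp[(25s₁ + 25s₂)/50] − 1. The single Poisson slope fitted to the expected counts gives:

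| s₁, s₂ | true | single slope | gap (points/year) |
|---|---|---|---|
| −2%, +1% | −0.50% | −0.55% | 0.05 |
| −2%, 0 | −1.00% | −1.06% | 0.06 |
| −3%, +1% | −1.00% | −1.12% | 0.13 |
| −3%, 0 | −1.49% | −1.63% | 0.14 |

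Gaps are computed before rounding. For scale, the Poisson 95% half-width is about 1.96/√(μΣt²), with t centred and Σt² = 51 × (51² − 1)/12 = 11,050. That is 0.19 points per year at μ = 100 and 0.13 at μ = 200.

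In these scenarios, with pure Poisson error and 50, 100 or 300 deaths in 1969, the Pearson dispersion about the single line is about 1.2-5.1. The actual standard deviation of the fitted slope is nevertheless only 0.95-1.15 times the Poisson standard error. The curvature is a fault in the mean model and barely affects the slope's sampling variance.

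**3. Age within a stratum.** Suppose rates in the 18-24 band rise 5-20% per year of age and the population's mean age within the band drifts by 0.16-0.4 years. A crude trend would then be off by 0.02-0.16 points per year over 50 years, against the half-width of 0.13-0.19. Over 19 years it would be off by 0.04-0.41. For the 20-year series Σt² = 20 × (20² − 1)/12 = 665, so the half-width is 1.4 (μ = 30) to 3.4 (μ = 5) and the shift is small. The under-18 band was not computed.

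**The case against.** The best defence has four parts.

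- **The model sentence describes how year is coded; it does not limit the model to year.** This stands. A reader might infer that year is the only term and that a crude trend is being tested, but the documents do not say so. The same paragraph is about age-adjusted rates, and splitting at 18 already removes confounding between the two bands. What remains is an incomplete specification: agreement with the plotted rates is possible but not assured.
- **Curvature does not make standard errors too small.** This also stands. A reader might take the square root of the dispersion about a single line, roughly 1.1 to 2.3 in the scenarios above, as the factor by which intervals are too short. The simulated slope standard deviation refutes that. Pearson scaling around a misfitting single line also over-covers (97-100%), so scaling does not repair curvature.
- **Alternatives are already in the plan.** Linear regression estimates its own residual variance, and joinpoint addresses change points. Both are discretionary, however. Linear regression is there for comparability, and nothing says which model supplies the reported AAPC.
- **The study's primary aim is descriptive and the counts are unknown.** Both are true, and they limit how firmly the size can be stated. But these trends carry intervals, P values and a significance threshold, and nothing committed in the plan would reveal overdispersion if it were present.

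**Conclusion.** The concern holds in a limited form and should be corrected before analysis. It concerns mainly the 1969-2019 mortality series, where the committed Poisson model has no dispersion allowance. For flat trends and 50-200 deaths per year per stratum, the error rate would be about 6-11% with 5% extra variation. With 10% it would be about 11-13% at 50 deaths, rising to about 26% at 200. Neither the counts nor the extra variation is in the documents. If the true extra variation is nil, so is the problem.

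It would be wrong to extend this to the incidence results for rare subtypes: at 2-10 cases per year the error rate stays at about 5-6%.

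The single-slope issue is distinct: a gap of about 0.05-0.15 points per year from the true average change, and only if the trend really bends in the way assumed. The age point is a gap in specification and not a demonstrated mismatch.

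**What to change.** Amend Section 10.2 to state that:

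1. the response is the annual count of cases or deaths, with log population as an offset;
2. calendar year is continuous and age is a factor within each of the <18 and 18-24 strata, using single years or roughly 5-year groups cut at 18;
3. standard errors are Pearson-scaled (quasi-Poisson) with a minimum scale of 1;
4. for 1969-2019 mortality, the joinpoint analysis is mandatory and the AAPC is taken from its segments.

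Step 4 matters for step 3: the scale should reflect variation about an adequate mean and not lack of fit to one straight line.

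The cost is a change to the model statement, using data sources already in the plan. Some intervals will widen. The minimum scale makes the test slightly conservative when there is no overdispersion: in simulation with 50-200 deaths per year it rejected about 3-4% of the time instead of 5%.
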